## 8. **RESEARCH QUESTION AND OBJECTIVES**

#### 8.1. Research Question

This post-authorization safety study (PASS) is an observational study of MM patients treated with ide-cel in the postmarketing setting to further investigate the research objective described in Section 8.2.

### 8.2. Research Objectives

#### 8.2.1. Primary Objective

• To characterize the incidence and severity of selected adverse drug reactions (ADRs), as outlined in the Summary of Product Characteristics (SmPC), in patients treated with idecel in the postmarketing setting and to monitor for potential clinically important adverse events that have not yet been identified as part of the ide-cel safety profile.

#### 8.2.2. Secondary Objective

• To assess survival in patients treated with ide-cel in the postmarketing setting.

## 9. **RESEARCH METHODS**

## 9.1. Study Design

This study is designed as a non-interventional cohort study that is part of multiple registries of patients with MM treated with ide-cel in the postmarketing setting which includes patients treated with out of specification (OOS) product.

Data from a total of 1000 patients treated with ide-cel, including a minimum of 300 EU patients, will be collected until death, lost to follow-up, or withdrawal of consent, or up to 15 years, whichever occurs first. This registry study is expected to require up to 5 years to select the planned 1000 patients.

No comparison groups will be defined and no inferential testing will be performed.

Secondary malignancies must be reported to the Sponsor by the treating physicians in order to expedite AE reporting. In the event that a secondary malignancy of T cell origin is suspected, the Sponsor should be contacted to obtain instructions on the collection and transfer of a tumor tissue sample for testing in a separate process, outside of this PASS. In the postmarketing setting, the Sponsor will offer transgene assay service testing for all secondary malignancies of suspected T cell origin where a sample is available, as a routine pharmacovigilance measure to ensure gathering the most information possible for clinical assessment of the reported spontaneous case.

#### 9.1.1. **Primary Safety Endpoint(s)**

Incidence and severity of selected AEs reported post ide-cel infusion:

- All secondary malignancies
- CRS Grade  $\geq 3$
- Neurotoxicity Grade  $\geq 3$
- Prolonged cytopenias
- Pregnancy outcome
- Other AEs considered related to ide-cel

#### 9.1.2. Secondary Effectiveness Endpoint(s)

- Overall survival (OS)
- Progression-free survival (PFS)

### 9.2. Setting

This noninterventional cohort study will be based on secondary data that are collected from existing independent registries, such as the EBMT and the CIBMTR. Both registries use electronic Registry Case Report Forms (CRFs) forms onto which data may be entered directly by the treating centers.

All patients included in the EBMT and the CIBMTR registries are treated by their physicians according to real-world clinical practice. Physicians are trained to identify and approach patients treated with at least one dose of ide-cel to obtain their written informed consent according to the registries' standard procedures, to transfer the data to the EBMT or the CIBMTR and to be shared with competent health authorities, MAH and other parties in line with the signed informed consent forms.

#### 9.2.1. Eligibility Criteria

All patients who meet the following eligibility criterion will be selected from the registries:

• Patient must have been treated with at least one infusion of ide-cel in the postmarketing setting. Patients treated with OOS product will also be eligible.

#### 9.3. Variables

The following variables will be recorded and used within this study:

Classification	Category	Variable	Description
		Patient Code / ID	Unique de-identified ID for patient
		Reporting Center (RC) Name / ID	Center name or ID reporting to the registry
Baseline (at infusion date)	General Identifiers	Manufacturing Site (MFS) Name /ID	Site name or ID producing the CAR T product
(at infusion date)		Apheresis Center (AC) Name / ID	Center name or ID conducting leukapheresis
		Site of Care (SC) Name / ID	Center name or ID treating patient and infusing the CAR T product
		Product Name	Name of CAR T product
Baseline	Product Information	Product Code / ID (Join ID)	Product ID for the first product
		Product Quality: OOS	Product: out of specification, yes/no
	Key Treatment Processes and Timing	Patient Registering Date	Date patient was registered into the registry DB by the RC
		Leukapheresis Date	Date blood was collected at the AC
		Blood Shipment Date	Date blood was shipped from the AC to the MFS
		Blood Arrival Date	Date blood arrived at the MFS
		Manufacturing Start Date	Date MFS started production of CAR T
		Manufacturing End Date	Date MFS completed production of CAR T
		Product Shipment Date	Date CAR T was shipped to the SC
Baseline		Product Receipt Date	Date CAR T arrived at the SC
		Lymphodepleting Therapy Date	Date when lymphodepleting therapy started at SC
		Infusion Date	Date when CAR T was infused to the patient at the SC
		Product Infusion Count	Infusion counting number and total number of infusions
		Diagnosis Date	Date when primary disease was diagnosed
		Last Contact Date	Date when patient was last time in contact with the SC
		Safety Assessment Date	Date of any safety assessments findings (as listed in the safety section below)
		Effectiveness Assessment Date	Date of any effectiveness assessments findings (as listed in the effectiveness section below)

Confidential and Proprietary

Table 4: Variables (Con	tinued)
-------------------------	---------

Classification Category		Variable	Description
		Age	Age at infusion (years)
		Weight	Body weight at infusion (kg)
Deseline	Democratica	Height	Body height at infusion (cm)
Baseline	Demographics	Gender	Gender of patient
		Country	Country of the infusion center
		Region	Region of treatment: North America/Europe/Japan/Rest of the World
		Karnofsky Performance Score	Karnofsky performance score at infusion
	Clinical Variables (Disease History/ Prior Therapy/ Infusion Related)	ECOG Performance Score	ECOG performance score at infusion
		Disease History/Co-Morbidity	Comorbidity prior to infusion and organ involvement (eg, cardiac, hepatic, obesity, pulmonary renal, diabetes, solid tumor, and others)
		Prior Therapy 1: Lines	Number of prior therapy lines
		Prior Therapy 2: List	Names of prior therapies (systemic therapies, standard regimens)
		Prior Therapy 3: HCT	Number of prior hematopoietic cell transplantations (HCTs)
Baseline		Prior Therapy 4: HCT Type	Types of prior HCTs
		Disease Status 1: Primary Disease	Primary disease and disease status prior to LD chemotherapy
		Disease Status 2: International Staging System	Classification according to albumin and beta 2 microglobulin levels into stages I, II or III
		Disease Status 3: Cytogen. FISH	Chromosome changes identified via FISH at diagnosis
		Disease Status 4: Cytogen. Karyotyping	Chromosome changes identified via karyotyping at diagnosis
		Lymphodepleting Treatment	Types and names of lymphodepleting chemotherapy agents

Classification	Category	Variable	Description
		Secondary Malignancies (SM)	Subsequent neoplasms assessment and types of SM reported during FU
		Cytokine Release Syndrome 1: Presence	Assessment and presence of CRS reported during FU
		Cytokine Release Syndrome 2: Grade	CRS grade
		Cytokine Release Syndrome 3: Symptoms	CRS symptoms: fever, hypotension, hypoxia
		Cytokine Release Syndrome 4: Therapy	CRS therapy: intraven. fluids, vasopressors, positive pressure vent support, other therapy, CRS resolution date
		Neurotoxicity 1: Presence	Assessment and presence of NT reported during FU
		Neurotoxicity 2: Grade	NT grade
Outcome (reported at 100 d,	Safety	Neurotoxicity 3: Symptoms	NT symptoms: consciousness, dysphasia, seizure, paraparesis, cerebral edema, hallucination, tremors, other neurologic symptoms
		Neurotoxicity 4: Therapy	NT therapy: antiepileptic and other therapy given, NT resolution date
		Prolonged Cytopenia 1: Presence	Neutrophil count $< 500/\text{mm}^3$ , platelet count $< 20 \text{ x } 10^9/\text{L}$
		Prolonged Cytopenia 2: Recovery	Neutrophil and platelet recovery
6 months, yearly)		Hypogammaglobulinemia 1: Presence	Assessment and presence of hypogammaglobulinemia during FU
		Hypogammaglobulinemia 2: Therapy	Hypogammaglobulinemia therapy (immunoglobulin replacement) and resolution
		Tumor Lysis Syndrome 1: Presence	Assessment and presence of TLS reported during FU
		Tumor Lysis Syndrome 2: Grade	TLS grade
		Organ Toxicity Grade $\geq 3$	AE/symptoms/type at heart, gastrointestinal, kidney, liver, lungs, musculoskeletal, neurologic and "other" reported during FU
		Aggravated graft-versus-host disease (GVHD)	Information regarding chronic and acute GVHD
		Infections	Types and sites of serious (ie, requiring treatment) infection reported during follow-up (1st-5th reported infection)
		Pregnancy Outcome	Pregnancy reported during FU for female and for male partner
		Concomitant Medication	Other systemic therapy (other than for CT/HCT) given for maintenance or consolidation reported during FU

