#### 9.6.4. Effectiveness Analysis

#### 9.6.4.1. Analysis of the Secondary Effectiveness Endpoints

- **Overall Survival (OS)**: Overall survival is defined as the time from the date of first infusion to the date of death due to any cause. All patients will be followed for survival information, regardless of whether they receive additional treatment post-infusion. Patients who are alive at last contact date will be censored at that time, but no censoring will be done for additional treatment.
- **Progression-Free Survival (PFS)**: PFS is defined as the time from the date of first idecel infusion to the date of event defined as the first documented relapse or progression or death due to any cause, whatever happens first. Patients who are alive at last contact date will be censored at that time, but no censoring will be done for additional treatment.
- **Time To Event (TTE) Analysis:** Kaplan-Meier estimates and the associated 95% CIs of the median, 25th and 75th percentile will be presented. The two-sided 95% CIs will be computed using the log-log transformation. The survivor function will be displayed graphically using a KM curve.

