#### 9.6.5.2. General Handling and Analysis of Symptoms or Adverse Events

The registry collection of safety data is specific to certain symptoms of toxicity associated with CAR T cell therapy and recorded as safety outcomes. These safety data include CRS, neurotoxicity, hypogammaglobulinemia, TLS, infections, prolonged cytopenias, organ toxicities and secondary malignancies. All of the above, except for the secondary malignancies, are collected in a calendar format in an aggregate and summarized form based on the prior reporting period. Secondary malignancies, pregnancies and any deaths are reported on an event driven form upon knowledge at the site of care (center).

The incidence of organ toxicities will be summarized by Medical Dictionary for Regulatory Activities (MedDRA) system organ class (SOC) and preferred term (PT). Organ toxicities will be graded using National Cancer Institute Common Terminology Criteria for Adverse Events (NCI CTCAE) Version 5.0 or higher. Only organ toxicities of Grade 3 (severe), Grade 4 (life-threatening), and Grade 5 (death) will be summarized in reports. A patient who reports multiple occurrences of an organ toxicity with the same SOC and PT is counted only once using the maximum severity grade for summaries. If a patient experiences the same organ toxicity more than once with different grades, then the event with the highest grade will be tabulated in "by grade" tables. If a patient experiences multiple organ toxicity under the same PT and SOC, then the patient will be counted only once for that PT (SOC).

The incidence of each AESI and of most frequent AEs ( $\geq 10\%$ ) will be summarized using the number and percentage of patients experiencing the event. Exact 95% Clopper Pearson CIs will be provided for the percentages.

Adverse Events will be reported according to the following structure:

1) **Overall Summary of Organ Toxicities/Symptoms:** Summaries of AEs will be produced overall as described above.

- 2) Summaries by System Organ Class and Preferred Term: Summary tables by SOC and PT of the number of events and the number, percentage and exact 95% Clopper Pearson CIs for patients having events will be presented separately for each of the event types.

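### Survivors are censored at last contact with the infusing centre, but deaths count on knowledge alone, so early overall survival estimates may be too low

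*Protocol*

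**What the plan says.** All references are to the protocol.

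- **Alive date.** Section 9.3, Table 4 defines Last Contact Date as "Date when patient was last time in contact with the SC". The Site of Care (SC) is the "Center name or ID treating patient and infusing the CAR T product". The Reporting Center is a separate field, the "Center name or ID reporting to the registry", so the variable list allows for information from a centre other than the SC.
- **Censoring.** Section 9.6.4.1 applies the same rule to OS and PFS: "Patients who are alive at last contact date will be censored at that time, but no censoring will be done for additional treatment".
- **OS event.** "Overall survival is defined as the time from the date of first infusion to the date of death due to any cause". Nothing requires the death to fall on or before the last contact.
- **PFS event.** "the first documented relapse or progression or death due to any cause".
- **How deaths arrive.** Section 9.6.5.2 says that "any deaths are reported on an event driven form upon knowledge at the site of care (center". Progression and relapse are not among its event-driven items.

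**The concern.** Alive status and death are ascertained under different stated rules. Being counted alive at a given time requires contact between the patient and one particular centre. Being counted dead requires only that the centre hears of it.

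Take a patient who moves to another hospital after infusion. If the infusing centre later learns that the patient died, the death enters at its date and all the time up to it is counted. If the patient is still living, follow-up stops at the last contact with the infusing centre, even if another source has reported the patient alive since. How long such a patient stays in the risk set then depends on whether the patient later dies. That is informative censoring, and it removes survivors selectively.

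OS is one of only two effectiveness endpoints, and follow-up is planned for up to 15 years. The cause is the definition itself, so more frequent or more complete forms would not remove it.

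**Working it through.** The protocol states no expected OS, no share of patients followed elsewhere and no share of off-site deaths learned of, so there is no figure of its own to reproduce. Every input below except the PFS median is an assumption.

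**1. Mechanism, by hand.** Suppose OS is exponential with a median of 20 months, so S(t) = 0.5^(t/20). Everyone leaves the SC at month 6, everyone has 60 months of potential follow-up, and every death is learned of.

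- S(6) = 0.812, S(36) = 0.287, S(60) = 0.125.
- True conditional survival from month 6 to month 36: 0.287 / 0.812 = 0.354.
- Under the stated rules, patients alive at month 60 are censored at month 6, so the risk set afterwards holds only those who die by month 60. Kaplan-Meier then estimates [S(36) − S(60)] / [S(6) − S(60)] = 0.162 / 0.687 = 0.236.
- Estimated 36-month OS: 0.812 × 0.236 = 0.192, against a true 0.287.

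If none of the later deaths is learned of, everyone who leaves is censored at month 6 whatever the outcome, and this bias is absent. The example is extreme because everyone leaves.

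**2. OS under milder assumptions.** Simulation of 200,000 patients, uniform entry over 5 years, data cut at year 5, exponential OS with a median of 20 months. A share f has its last SC contact uniformly between 3.3 and 12 months, independent of prognosis. A share q of off-site deaths reaches the SC.

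| f | q | Estimated median (true 20) | 36-month OS (true 0.287) |
|---|---|---|---|
| 0 | – | 20.0 | 0.289 |
| 25% | 0 | 20.0 | 0.287 |
| 25% | 50% | 19.1 | 0.263 |
| 25% | 100% | 18.5 | 0.245 |
| 50% | 0 | 20.1 | 0.289 |
| 50% | 50% | 18.1 | 0.232 |
| 50% | 100% | 17.1 | 0.197 |

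With f = 50% and q = 100%, a true median of 12 months is estimated as 11.3, and one of 30 months as 23.1. The f = 0 row corresponds to the proposed fix. At true medians of 12, 20 and 30 months it returns 11.9, 20.0 and 29.9.

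**3. Dependence on the data cut.** A second simulation used a median of 2 years, 20% to 40% leaving between months 3 and 12, and all deaths known.

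| Cut | Time | True OS | Estimated OS (20% to 40% leaving) |
|---|---|---|---|
| Year 5 | 2 years | 50% | 47% to 44% |
| Year 5 | 4 years | 25% | 21% to 17% |
| Year 10 | 2 years | 50% | 49% in either case |
| Year 10 | 5 years | 18% | 16% to 15% |

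The bias shrinks because only patients alive at the cut are wrongly censored. With entry uniform over 5 years and survival 0.5^(u/2), the share alive is:

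- cut at year 5: (1 − 0.5^2.5) / (2.5 ln 2) = 0.823 / 1.733 = 48%;
- cut at year 10: (0.5^2.5 − 0.5^5) / (2.5 ln 2) = 0.146 / 1.733 = 8%;
- cut at year 15: (0.5^5 − 0.5^7.5) / (2.5 ln 2) = 0.026 / 1.733 = 1.5%.

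**4. PFS.** The median of 8.6 months comes from the Phase 2 study in Section 7.2.3, giving a true 24-month PFS of 0.5^(24/8.6) = 0.145. Assume f = 50% and a median survival after progression of 12 months.

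| Off-site deaths known | Off-site progressions reported | Median | 24-month PFS |
|---|---|---|---|
| all | all | 8.4 | 0.118 |
| all | half | 8.7 | 0.149 |
| all | none | 9.1 | 0.186 |
| none | none | 8.6 | 0.147 |

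The bias can go either way.

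**The case against.** The strongest reply is that the asymmetry is conditional. Deaths also reach the registry through the site of care, so alive status and death share one channel, and the protocol describes no second route that carries deaths only. Contact is not the same as a visit: a call or letter to the centre could qualify. Section 9.6.4.1 says that every patient is followed for survival. Section 9.8 already warns that gaps and attrition can bias time-to-event results, and the SAP, which is not shown, could derive a better alive date.

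Much of this stands. The bias needs some off-site deaths to become known, remote contact by the SC would reduce it, and its size is unknown. If sicker patients left and their deaths were missed, OS would be biased upward instead.

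The reply does not remove the point. The channel is shared, but the conditions differ: knowledge is enough for a death, while the alive date needs contact. A general intention to follow survival does not change the date at which the same section censors. Section 9.8 discusses missing data, irregular assessment dates and poorly captured mortality, not an alive date restricted to one centre. And Table 4 and Section 9.6.4.1 state the rule outright, so this is not detail left for the SAP.

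A reader might infer three stronger claims that the documents do not support:

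- **That PFS is also biased downward.** Off-site progression may go unreported, and the direction then changes.
- **That a patient with a recorded death would be censored** because the patient was alive at the last contact. This is strained, given that OS runs to death from any cause without restriction.
- **That the secondary-malignancy rate is inflated.** This would follow only if the same date closed person-time and off-site malignancies were captured. Section 9.6.5.1 leaves the rate methods to the SAP.

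**Conclusion.** The point holds for OS, conditionally. The alive date is tied to the infusing centre and the death date is not. OS is therefore biased downward to the extent that off-site deaths become known and leaving the centre is unrelated to prognosis. If no off-site death is learned of, this bias is absent.

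Under the assumptions shown, an analysis at the end of a 5-year accrual period understates 2-year OS by 3 to 6 percentage points and 4-year OS by 4 to 8. With a cut at year 10 the 2-year figure is off by about 1 point. The year-5 interim report is thus the most exposed, and a reader should not infer a material distortion of the final analysis: at a 2-year median with all deaths known, few patients are still alive to be mis-censored. None of these sizes can be derived from the documents, which give neither the share followed elsewhere nor the completeness of death reporting. The direction for PFS is undetermined. OS is a secondary, descriptive endpoint, which limits the consequence.

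**What to change.** 1. In Table 4, redefine Last Contact Date, or preferably add a derived variable, as the latest date on which the patient is known to be alive from any source reaching the registry (infusing centre, reporting centre, referring physician).
2. In Section 9.6.4.1, censor OS at that date for patients with no recorded death, and take deaths and alive dates to the same data cut.
3. Do not carry this date over to PFS. The PFS rule now uses the same last contact date, so redefining that variable alone would extend PFS follow-up through periods in which off-site progression may be unreported. A separate derived variable used only for OS avoids this. Otherwise the PFS sentence needs its own censoring date.

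The cost is wording in two places and one derivation in the analysis data sets that the sponsor already plans to build (Section 9.4). No new patients, visits or registry forms are needed.

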## 7.2. Background

Multiple myeloma (MM) accounts for approximately 10% to 18% of hematologic malignancies (Moreau, 2017; Siegel, 2020) and primarily affects older individuals. In Europe, the median age at onset of MM is 72 years (Moreau, 2017); MM is very rare in patients younger than 40 years old (Howlader, 2019). The number of MM patients is increasing in the general population due to aging populations and more patients living longer due to modern antimyeloma therapies (AMTs) (Turesson, 2018). The prevalence of MM varies from country to country in the EU. Overall, the estimated prevalence of MM in the EU in 2018 ranged from 1.79 to 3.61 in 10,000 persons (data on file). In Europe, 48,297 new cases of MM were estimated in 2018 (International Agency for Research on Cancer [IARC], 2019).

Multiple myeloma is a largely incurable blood cancer characterized by the clonal proliferation of malignant plasma cells both within the bone marrow and at localized extramedullary sites termed plasmacytomas (Rajkumar, 2016). The malignant proliferation of the plasma cell clone causes increasing levels of monoclonal protein (M-protein) in the serum and urine and may result in bone marrow failure, suppression of uninvolved immunoglobulin levels, and skeletal destruction. Clinical complications of progressive MM include recurrent infections, cytopenias, renal failure, hyperviscosity syndrome, hypercalcemia, bone pain, and pathologic fractures (Munshi, 2012).

The course of MM is characterized by a period of disease control after initial therapy followed by progression, typically with subsequently shorter periods of response and relapse with each successive therapy (Larocca, 2017; Moreau, 2017). With each relapse and each subsequent line of AMT, tumors typically recur more aggressively, leading to shorter response duration and ultimately, refractory MM, which is associated with shortened survival times (Gandhi, 2019; Kumar, 2017; Yong, 2016). Furthermore, each line of therapy is associated with an increased risk of comorbidities, including treatment- and disease-related complications (Leleu, 2019; Song, 2016).

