#### 9.6.3. Baseline and Demographic Characteristics

Patients are included into the registry from 2 weeks prior to the ide-cel infusion to any time afterwards. Baseline data are retrospectively reported by data managers after the administration of ide-cel and are collected only once. All information, including any medical history and measurements done prior to the administration of ide-cel, becomes available in the registry as baseline data.

The baseline data will be summarized using descriptive statistics. Individual patient listings will also be provided to support the summary tables. The number and percentage of patients in each of the categories, as listed in Section 9.3, will also be given.

The following baseline data will be presented:

- **Demographics:** Demographic information collected at baseline will be presented using descriptive statistics.
- **Disease History/Comorbidities**: The frequency of patients with at least one comorbidity, as well as frequency counts of different comorbidities will be presented. The ECOG Performance Status score and disease status at infusion will be summarized by frequency counts.
- **Prior Therapy/Prior Medications**: Number of lines of prior therapies will be presented using descriptive statistics. Number of lines of prior therapies will be described as frequency counts. A frequency tabulation of the number of patients with the different types of prior therapies will be given. Also, a frequency tabulation of whether the patient had prior hematopoietic cell transplantations (HCTs) and the types of prior HCTs will be given.
- Lymphodepleting Treatment: A frequency tabulation of the list of lymphodepleting agents will be given.

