#### 9.6.5. Safety Analysis

#### 9.6.5.1. Analysis of the Primary Safety Endpoints

The primary endpoint is the incidence and severity of the following selected AEs reported post ide-cel infusion. These AEs are equivalent to the AESIs:

- All secondary malignancies
- CRS Grade  $\geq 3$

- Neurotoxicity Grade  $\geq 3$
- Prolonged cytopenias
- Pregnancy outcome
- Other AEs considered related to ide-cel treatment, for example:
  - o hypogammaglobulinemia
  - $\circ$  tumor lysis syndrome (TLS) Grade  $\geq$  3
  - serious infections (ie, requiring treatment)
  - $\circ$  organ toxicities Grade  $\geq 3$
  - others (eg, aggravated GVHD)

The primary endpoints will be analyzed and reported as described in Section 9.6.5.2 (below). Furthermore, suitable measures (incidence proportions and incidence rates) will be calculated with the appropriate time periods and methods. Analyses will be carried out without accounting for competing risks as well as accounting for competing risks using the cumulative incidence function method. Details are described in the SAP.

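### Hypogammaglobulinemia is analysed as incident after ide-cel, but Table 4 records only its presence in follow-up and no baseline status, so pre-existing cases can be counted as new

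*Protocol*

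**What the plan says.** Section 9.6.5.1 sets the measure: "The primary endpoint is the incidence and severity of the following selected AEs reported post ide-cel infusion". Hypogammaglobulinemia is the first item under "Other AEs considered related to ide-cel treatment, for example". The section equates the listed events with the AESIs and calls for incidence proportions, incidence rates and cumulative incidence functions. Under Section 9.6.5.2 each AESI is "summarized using the number and percentage of patients experiencing the event", with exact Clopper-Pearson intervals.

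In the outcome block of Table 4 (Section 9.3) the variable is "Assessment and presence of hypogammaglobulinemia during FU", reported at 100 days, 6 months and yearly. A second variable covers immunoglobulin replacement and resolution. Section 9.6.5.2 adds that these safety data "are collected in a calendar format in an aggregate and summarized form based on the prior reporting period".

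The baseline block of Table 4 has performance scores, comorbidity, prior therapy, staging, cytogenetics and lymphodepleting treatment. It names no immunoglobulin level, no hypogammaglobulinemia status and no prior immunoglobulin replacement. The only laboratory values behind the staging variable are albumin and beta 2 microglobulin.

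On the disease itself, Section 7.2 says that the malignant clone "may result in bone marrow failure, suppression of uninvolved immunoglobulin levels, and skeletal destruction".

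**The concern.** An incidence measure needs patients who are free of the condition at the start of the risk period, or at least a rule for those who are not. Here the risk period starts at infusion, the recorded fact is presence at some later time, and the protocol itself names the underlying disease as a cause of the condition. The only eligibility criterion (Section 9.2.1) is at least one postmarketing infusion, so patients already affected are included.

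The reported percentage can therefore mix two quantities: patients who developed hypogammaglobulinemia after ide-cel, and patients who had it beforehand and still have it. Only the first answers the primary objective of characterising adverse drug reactions. In a single-arm study no comparison group would expose the mixture, and with 1000 patients the interval would be narrow around the wrong quantity.

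**Working it through.** The protocol states no figure for hypogammaglobulinemia, so there is none to reproduce. The check has two parts.

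**1. Can any listed variable separate new from pre-existing cases?**

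- Follow-up presence (Table 4, outcome block): no onset or worsening criterion is attached.
- Safety assessment date (Table 4): this dates a finding. It does not show that the patient was unaffected at infusion.
- Comorbidity (Table 4, baseline block): the examples are organ conditions, diabetes and solid tumor, with an open remainder. Immunoglobulin status is not named.
- Staging: albumin and beta 2 microglobulin only.
- Relatedness: Section 9.6.5.1 refers to events considered related, but Table 4 lists no causality variable through which that could be applied.

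No listed variable does the job.

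**2. How large could the effect be?** All inputs here are assumptions, because the protocol gives no baseline prevalence and no new-onset risk.

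- p = share already affected at infusion
- r = new-onset risk among the rest
- s = share of pre-existing cases that persist, are reported in follow-up and are counted

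Reported proportion = p·s + (1-p)·r, so reported minus r = p·(s - r).

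With s = 1 (every pre-existing case counted), reported = p + (1-p)·r:

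| p | r | Reported | Reported / r | Excess over r | Pre-existing share of counted cases, p / reported |
|---|---|---|---|---|---|
| 20% | 20% | 0.20 + 0.80 × 0.20 = 36% | 1.8 | 16 points | 56% |
| 40% | 20% | 0.40 + 0.60 × 0.20 = 52% | 2.6 | 32 points | 77% |
| 60% | 20% | 0.60 + 0.40 × 0.20 = 68% | 3.4 | 48 points | 88% |
| 20% | 70% | 0.20 + 0.80 × 0.70 = 76% | 1.09 | 6 points | 26% |
| 40% | 70% | 0.40 + 0.60 × 0.70 = 82% | 1.17 | 12 points | 49% |
| 60% | 70% | 0.60 + 0.40 × 0.70 = 88% | 1.26 | 18 points | 68% |

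The ratio depends heavily on r, so no single multiple can be defended.

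For precision at n = 1000, the approximate half-width is 1.96 × √(q(1-q)/1000). This is 3.0 points at q = 0.36 and 2.0 points at q = 0.88. The interval would not reveal an excess of the sizes shown.

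At the other extreme, suppose a relatedness judgement removed every pre-existing case (s = 0) while the denominator stayed at all patients. The result would be (1-p)·r, for example 0.60 × 0.20 = 12% at p = 40% and r = 20%. That is new onset as a share of everyone, not the 20% risk among those who could develop it. Without baseline status a reader cannot tell where between 12% and 52% the reported figure lies.

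**The case against.** The strongest reply is that the endpoint item covers events considered related to ide-cel, not mere presence, so a clinician would not report long-standing hypogammaglobulinemia. Part of this stands. A reader might infer that a patient on replacement before infusion is bound to be counted at the 100-day report, and no passage says that. But the wording does not cure the problem, because no listed variable records the judgement and Table 4 describes the outcome as presence.

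The second reply is that the data may be obtainable. Section 9.6.3 says that medical history and "measurements done prior to the administration of ide-cel, becomes available in the registry as baseline data". The abstract's list of data is expressly not exhaustive, and Section 9.4 provides for derived variables and further covariates. This stands. A reader might infer that the SAP could not repair the gap, but the documents leave room for a later data specification to request the values. Against that, Section 9.3 introduces Table 4 as the variables to be recorded and used, and neither it nor the baseline summaries in Section 9.6.3 selects immunoglobulin status. Since the data come from independent registries, availability should be confirmed and not presumed.

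Third, hypogammaglobulinemia is one example within the last endpoint item and is not separately named in Section 9.1.1. The study is also descriptive. Both facts limit the weight of the point.

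A reader might also extend the argument to prolonged cytopenias, for which baseline counts are likewise not listed. The documents do not support that extension. The Table 4 thresholds are severe (neutrophils below 500/mm³, platelets below 20 × 10⁹/L), there is a separate recovery variable, and nothing shows that patients are infused with counts already below those limits.

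**Conclusion.** The point holds as a modest design gap. The plan analyses hypogammaglobulinemia as incident within the primary endpoint, defines it by presence in follow-up, and lists no baseline variable that would identify patients already affected by a condition the protocol attributes in part to the disease. Pre-existing cases can therefore be counted as incident.

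The direction is upward if most pre-existing cases persist and are counted (s greater than r). The size is unknown. Under full persistence and assumed p of 20% to 60%, the reported proportion is 1.8 to 3.4 times the new-onset risk at r = 20% and about 1.1 to 1.3 times at r = 70%. These are illustrations over assumed inputs, not estimates for this study.

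It would go too far to say that the figure is simply prevalence, or that a substantial share of patients enters already affected. Section 7.2 says only that suppression may occur and gives no frequency.

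**What to change.** - **Table 4, baseline block.** Add hypogammaglobulinemia status (or the last immunoglobulin level before lymphodepletion) and prior immunoglobulin replacement (yes/no), for each registry that holds them. Use the same definition before and after infusion.
- **Section 9.6.5.1.** Report new onset among patients free of the condition at baseline, alongside presence during follow-up for all patients, with a row for unknown baseline status.
- **Where a registry does not hold the baseline value.** Label the figure as presence during follow-up, not incidence, and add the limitation to Section 9.8, which does not mention it now.

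The cost is two extracted baseline fields if the registries hold them, and one further table. The at-risk denominator becomes smaller, so the new-onset interval is somewhat wider, and some patients will fall in the unknown row. If the fields are not held, the cost is a change of label and a sentence in the limitations.
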